Subjects will take ifetroban or placebo daily for 4 weeks and will continue taking daily montelukast. There will be a telephone encounter (**Phone Call 2**) 1 week into this Treatment Period to ensure safety and confirm that chronic asthma symptoms have not worsened.

After the 4-week treatment period, subjects will come into the ARC for **Visit 2**. Before aspirin is given, interval history, physical exam, ACQ, SNOT-22, TNSS, and spirometry will be recorded, along with FeNO, and a urine sample will be collected for pregnancy and eicosanoid metabolites. Nasal lavage and a nasal epithelial scraping sample will also be taken (prior to the TNSS questionnaire to ensure that the procedures do not affect the symptom assessment), along with a blood draw for CBC/differential and cellular assays. After waiting at least 15 minutes following the nasal lavage and scraping so that any nasal irritation has subsided, subjects will then undergo an oral aspirin desensitization procedure. They will receive an initial 40.5 mg dose of aspirin, and then every 90 minutes will be given increasing doses of 81, 162, and 325 mg aspirin. Vital signs are obtained every 90 minutes during the aspirin challenge/desensitization. If at any point the subject develops symptoms of a reaction, we will examine them and record the time of onset of reaction. The dose of reaction that induces an increase in TNSS of 2 or more points will be recorded as the provocative dose.

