Following the onset of reaction, patients will be observed for a 3-hour period, during which time no more aspirin doses will be given. TNSS will be recorded at the onset of reaction and again every 30 minutes during this 3-hour period after reaction. Pulmonary function testing is repeated before each dose and at the onset of reaction and if it remains within 85% of their pre-challenge FEV₁, it will be repeated every 90 minutes during the 3-hour period after reaction. If the FEV₁ falls by 15% or more from their morning FEV₁, they will be treated with albuterol, administered by metered dose inhaler (MDI), (up to 8 puffs per administration), and FEV₁ will be repeated every 30 minutes until it has returned to within 85% of their morning pre-challenge FEV₁. If after 3 rounds of albuterol administered by MDI (a total of 24 puffs), the subject's FEV₁ has not returned to within 85% of their morning pre-challenge FEV₁, nebulized albuterol will be administered. No medications (except albuterol and ipratropium) will be used for relief of symptoms during the desensitization until the 3-hour period of observation following onset of reaction is completed, unless required for a patient's safety. A blood sample will be collected 1 hour after the onset of reaction for CBC/differential, platelet activation assays, and platelet-leukocyte aggregate measurements. Urine and nasal samples will be collected at the onset of reaction, and again 90 minutes and 3 hours after the onset of reaction, or if there is no clinical reaction at all, will be collected 90 minutes after the 325mg dose of aspirin is given.

Upon completion of the 3-hour period of observation, further aspirin doses will be administered every 90 minutes until a state of clinical desensitization to and tolerance of 325 mg of aspirin is achieved. Patients will be discharged home 90 minutes after ingestion of 325 mg of aspirin and will be instructed to begin taking daily aspirin, as is part of our standard-of-care for these patients. If required due to time constraints, this visit could proceed onto the next day, during which the subject would begin by repeating the aspirin dose they ended with the day before. However, 95% of our aspirin desensitization procedures done as part of clinical patient care are completed within the first day.

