3.2. Primary Outcome

The primary outcome is the calculated dose of aspirin that induces an increase in the Total Nasal Symptom Score (TNSS) of 2 from the baseline value, or “PD₂”.

The PD₂ will be calculated during the aspirin desensitization at Visit 2 as follows:

$$inverselog_{10} \left(\frac{(2 - (PrevTNSS - BaselineTNSS)) \times (\log_{10} ProvocDose - \log_{10} PrevDose)}{(MaxTNSS - BaselineTNSS) - (PrevTNSS - BaselineTNSS)} + (\log_{10} PrevDose) \right)$$

Where:

Baseline TNSS = TNSS score prior to administration of aspirin

PrevTNSS = TNSS score immediately previous to onset of aspirin reaction

MaxTNSS = Maximum TNSS score recorded during 3-hour observation period during aspirin reaction

ProvocDose = Dose of aspirin that provoked a reaction

PrevDose = Dose of aspirin that preceded the provocative dose

We have used this outcome in our current nearly completed study of 40 patients with AERD and have found that it is an accurate reflection of reaction severity and aspirin sensitivity. As PD₂ is based both on the provocative dose of aspirin that induced a reaction and on the severity of the reaction, it reflects each patient’s sensitivity to aspirin. Nasal and upper respiratory symptoms (congestion, rhinorrhea, sneezing, nasal and ocular itching) in response to the provocative dose of aspirin will be monitored based on a 0- to 5-point scale (0, none; 1, little; 2, moderate; 3, quite a bit; 4, severe; 5, very severe) as described.³¹ The maximum TNSS possible (indicating maximal symptoms) is 40.

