4.2. Inclusion Criteria

Individuals who meet all of the following criteria are eligible for enrollment as study participants:

1. Subject must be able to understand and provide informed consent
2. Age between 18 and 70 years
3. History of AERD, defined as meeting the diagnostic triad with:
 - a. History of physician-diagnosed asthma **and**
 - b. History of physician-diagnosed nasal polyposis **and**
 - c. History of pathognomonic reactions to aspirin or other nonselective COX inhibitors.

To ensure all patients stringently meet this criteria and truly have AERD, we will require that patients either:

1. Have a history of at least two pathognomonic clinical reactions to aspirin or other nonselective COX inhibitors with features of lower (cough, chest tightness, wheezing, dyspnea) and/or upper (rhinorrhea, sneezing, nasal obstruction, conjunctival itching and discharge) airway involvement.
Or...
2. Have had a confirmatory physician-administered challenge with aspirin or another nonselective COX inhibitor that induced a pathognomonic respiratory reaction as above.

4. Stable asthma (post-bronchodilator FEV₁ of $\geq 70\%$, no glucocorticoid burst (increase $\geq 10\text{mg}$ per day or doubling daily dose, whichever is less) for at least 2 weeks prior to Visit 1, and no hospitalizations or ER visits for asthma for at least 6 months prior to Visit 1), and for those patients on daily oral steroids, they must require no more than a daily dose of 10mg prednisone or equivalent for their standard daily therapy to be considered for inclusion.
5. For females: Non-pregnant and practicing adequate birth control or abstinence
6. For males: practicing adequate birth control or abstinence
7. No current smoking (not more than one instance of smoking in the last 3 months)

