5.4. Risks of Study Procedures

Risks of aspirin desensitization procedure. All individuals with AERD will experience a clinical reaction to aspirin, most often at a dose of 81 mg or below. By using the modified Scripps Institute protocol,³² limiting the study to individuals with stable asthma and no history of life-threatening reaction to COX inhibitors, and administering montelukast to all individuals undergoing the challenge, the procedure can safely be done in an ambulatory setting and is routinely performed in the Allergy Clinic at the BWH. To ensure safety of the challenge, vital signs will be obtained every 90 minutes, and patients are instructed to report any of the following symptoms; cough, dyspnea, chest tightness, rhinorrhea, congestion, sneeze, ocular pruritis and discharge. Spirometry is repeated before each dose, or at the time symptoms are reported. A decrease in pre-challenge FEV₁ of 15% or more is considered indicative of a positive lower respiratory tract reaction. In our experience, ~60% of individuals with AERD who are treated with montelukast develop airflow obstruction of this magnitude, while the remainder experience a reaction confined to the sinonasal tract. In addition to respiratory symptoms, occasionally extrapulmonary symptoms occur as well, which can include gastrointestinal manifestations (abdominal discomfort, nausea, vomiting, or diarrhea) and skin manifestations (flushing, itching, and rash). Systemic reactions that involve the cardiovascular system are very rare in this selected population.

Injectable adrenalin, oxygen, and resuscitation equipment are present in the ARC in the unlikely event of a systemic reaction, as are physicians skilled in resuscitation.

Risks of ACQ, SNOT-22, and TNSS questionnaires. There are no risks associated with questionnaires.

Risk of blood draw. Risks associated with drawing blood include some pain when the needle is inserted. There is a small risk of bruising and/or infection at the place where the needle enters the arm. Some people may experience lightheadedness, nausea or fainting. It is possible to develop an infection, but this is rare and can be treated.

Risk of spirometry. Occasionally, individuals may develop a slight dizzy feeling and/or temporary cough and/or chest discomfort when performing breathing tests. These tests are used in hundreds of laboratories throughout the world on a daily basis without harmful effects.

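### The provocative dose is defined in two ways; for a reaction with a TNSS rise below 2, the primary endpoint PD2 is missing, extrapolated above the reacting dose, or undefined

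*Combined protocol and SAP*

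**What the plan says.** Section 3.1, repeated in the Visit 2 steps of 8.3, defines the provocative dose by a nasal threshold: "The dose of reaction that induces an increase in TNSS of 2 or more points will be recorded as the provocative dose". Sections 3.2 and 13.2, which give the PD2 formula, define the same input without a threshold: "ProvocDose = Dose of aspirin that provoked a reaction". The other two scores are also tied to the reaction and not to a minimum rise: "PrevTNSS = TNSS score immediately previous to onset of aspirin reaction" and "MaxTNSS = Maximum TNSS score recorded during 3-hour observation period during aspirin reaction".

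A reaction is not recognised through TNSS alone. Section 3.1 states: "If at any point the subject develops symptoms of a reaction, we will examine them and record the time of onset of reaction". It continues: "Following the onset of reaction, patients will be observed for a 3-hour period, during which time no more aspirin doses will be given". Section 5.4 says that an FEV1 fall "of 15% or more is considered indicative of a positive lower respiratory tract reaction". Inclusion criterion 3 in Section 4.2 accepts qualifying past reactions "with features of lower (cough, chest tightness, wheezing, dyspnea) and/or upper" airway involvement. The TNSS items listed in 3.2 are nasal and ocular only.

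No section says what PD2 is when a reaction occurs with a TNSS rise of 0 or 1. Analysis populations (13.4.1) and supportive analyses of the primary endpoint (13.4.3) are both marked as not applicable.

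**The concern.** The two definitions agree whenever the reaction brings a TNSS rise of at least 2. They part when reaction symptoms pause dosing but the nasal score rises by less than 2, as in a reaction that is mainly bronchial. Under 3.1 and 8.3 that patient has no provocative dose, so PD2 cannot be computed. Under 3.2 and 13.2 the dose is defined, but the formula no longer interpolates between two doses: it projects beyond the reacting dose or fails.

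This affects the single primary endpoint, which is compared by an untransformed t-test with 20 patients per arm, where a few unusual values matter. The provocative dose is also the covariate for the aspirin-reaction analyses in 3.3 and 3.4. Without a rule, the scoring of these patients would be settled after their data are seen.

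**Working it through.** **Inputs.** Dose steps 40.5, 81, 162 and 325 mg (3.1, 8.3). PD2 formula (3.2, 13.2). Planning values (13.4.2): mean 60, SD 42 for placebo; mean 180, SD 170 for ifetroban; 20 per arm; two-sided 0.05; unequal-variance t-test. The number of affected patients is not given; one or two of 20 is an assumption.

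**1. The plan's own figure.** SE = √(42²/20 + 170²/20) = √(88.2 + 1445.0) = 39.16. Noncentrality = 120/39.16 = 3.065, with 21.3 Satterthwaite degrees of freedom. Power is 83.2%, which matches the stated 83%.

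**2. The formula.** Let p = PrevTNSS − BaselineTNSS and m = MaxTNSS − BaselineTNSS. Then

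log10 PD2 = log10 PrevDose + [(2 − p)/(m − p)] × log10(ProvocDose/PrevDose).

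For p below 2, the bracket is 1 when m = 2 (PD2 equals ProvocDose), below 1 when m exceeds 2 (interpolation), above 1 when m lies between p and 2 (extrapolation), and undefined when m = p. With p = 0 and m = 1 it is 2, so PD2 = ProvocDose²/PrevDose: 81²/40.5 = 162, 162²/81 = 324, 325²/162 = 652.

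| p | m | Reaction at 81 mg | At 162 mg | At 325 mg |
|---|---|---|---|---|
| 0 | 4 | 57.3 | 114.6 | 229.5 |
| 0 | 3 | 64.3 | 128.6 | 257.7 |
| 0 | 2 | 81 | 162 | 325 |
| 0 | 1 | 162 | 324 | 652 |
| 0 | 0 | none (0 in denominator) | none | none |
| 1 | 1 | none | none | none |

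If the maximum falls below the previous score (p = 1, m = 0), the bracket is −1 and PD2 drops below PrevDose, for example 162²/325 = 80.8 mg for a reaction at 325 mg.

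**3. Under the 3.1 definition.** ProvocDose does not exist, so there is no PD2. If such patients were dropped, power at the planning values would be 78.8% with 18 per arm and 73.3% with 16. Those losses are assumed.

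**4. Effect on an arm of 20.** Take 20 − k patients with mean 60 and SD 42, and k patients scored x. Mean = [(20 − k)×60 + k×x]/20. SD = √{[(19 − k)×42² + k(20 − k)/20×(x − 60)²]/19}.

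- k = 1, x = 162: mean 1302/20 = 65.1; SD √(41,635.8/19) = 46.8.
- k = 2, x = 162: mean 70.2; SD 50.6.
- k = 1, x = 324: mean 1464/20 = 73.2; SD √(97,963.2/19) = 71.8.
- k = 2, x = 324: mean 86.4; SD 90.4.

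The same calculation in the ifetroban arm (180, 170) with one value of 324 gives mean 187.2, SD 168.6, almost no change. One ifetroban patient scored 652 and not 325 raises that arm's mean by (652 − 325)/20 = 16.4 mg, against a planned difference of 120 mg.

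**The case against.** The strongest reply is that 3.1 governs: it says which dose is recorded as provocative, and the entry in 3.2 is shorthand for it. On that reading the maximum rise is always at least 2 and PD2 never exceeds the reacting dose. This is a fair reading, and it removes the extrapolation, but it leaves the patient with no primary endpoint and no rule for that.

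The second reply is that such patients may be rare. Section 5.4 says about 60% of montelukast-treated patients obstruct and the rest react only in the sinonasal tract; it describes no bronchial-only group, and it presents gut and skin symptoms as additional to respiratory ones. The wording in 4.2 concerns past reactions, not Visit 2. Section 1.1 says CysLT1R antagonists do not prevent sinonasal and ocular features. Two points is a low bar on a 40-point scale when the maximum is taken over readings every 30 minutes for 3 hours. All of this stands, and it limits the likely size.

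Third, PD2 is by definition a nasal quantity, so a value above a dose that raised TNSS by only 1 points in the right direction, and bronchoconstriction has its own secondary endpoint. That is true, but 652 mg lies at twice the top dose given, and a zero denominator has no direction.

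A reader might also infer that a later dose, given after the pause, could become the provocative dose. The documents do not support this: 8.3 treats the provocative dose as already fixed when it is repeated, and MaxTNSS comes only from the 3-hour observation.

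**Conclusion.** The inconsistency is real and lies in the inputs to the primary endpoint. For a reaction with a maximum TNSS rise below 2, PD2 is missing under one definition. Under the other it is about twice the reacting dose (rise of 1, no prior rise) or undefined (no rise above the previous score). The bronchial case is well supported as possible; an isolated extrapulmonary one is weakly supported.

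The effect on the trial is unknown because the frequency is not stated. One placebo patient of 20 moves the arm to about mean 65, SD 47 if scored 162, or about mean 73, SD 72 if scored 324. The smaller shift is the more typical, since 5.4 places most reactions at 81 mg or below.

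A reader might conclude that bronchial reactors are definitely scored as more aspirin-tolerant, or that the comparison is biased towards ifetroban. Neither follows. The first depends on choosing the 3.2 reading. The second needs such reactions to be more frequent on ifetroban, which fits the hypothesis but is not shown. Reactions at the first dose and patients who never react are separate gaps.

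**What to change.** Reconcile 3.1, 3.2, 8.3 and 13.2 so that ProvocDose has one meaning for the analysis. Before unblinding, add an analysis-only rule to 3.2 and 13.2:

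- When the maximum TNSS rise from baseline in the 3-hour observation period is below 2, do not apply the formula; set PD2 to the dose at which the reaction occurred.
- Do not use any dose given after that period in PD2.
- Report the number of patients scored this way in each arm.

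The clinical definition of a reaction, the dosing pause and the repeat dosing should not be altered by this change; those passages need only be made consistent with each other.

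The cost is wording. The downside is small: in these few patients PD2 becomes a conservative capped value and not a true nasal PD2. The cap does not equate types of reaction, since a nasal reactor at 81 mg with a rise of 4 scores 57 and a capped patient scores 81. It does keep every such value defined and within the doses given.

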3.2. Primary Outcome

The primary outcome is the calculated dose of aspirin that induces an increase in the Total Nasal Symptom Score (TNSS) of 2 from the baseline value, or “PD₂”.

The PD₂ will be calculated during the aspirin desensitization at Visit 2 as follows:

$$inverselog_{10} \left(\frac{(2 - (PrevTNSS - BaselineTNSS)) \times (\log_{10} ProvocDose - \log_{10} PrevDose)}{(MaxTNSS - BaselineTNSS) - (PrevTNSS - BaselineTNSS)} + (\log_{10} PrevDose) \right)$$

Where:

Baseline TNSS = TNSS score prior to administration of aspirin

PrevTNSS = TNSS score immediately previous to onset of aspirin reaction

MaxTNSS = Maximum TNSS score recorded during 3-hour observation period during aspirin reaction

ProvocDose = Dose of aspirin that provoked a reaction

PrevDose = Dose of aspirin that preceded the provocative dose

We have used this outcome in our current nearly completed study of 40 patients with AERD and have found that it is an accurate reflection of reaction severity and aspirin sensitivity. As PD₂ is based both on the provocative dose of aspirin that induced a reaction and on the severity of the reaction, it reflects each patient’s sensitivity to aspirin. Nasal and upper respiratory symptoms (congestion, rhinorrhea, sneezing, nasal and ocular itching) in response to the provocative dose of aspirin will be monitored based on a 0- to 5-point scale (0, none; 1, little; 2, moderate; 3, quite a bit; 4, severe; 5, very severe) as described.³¹ The maximum TNSS possible (indicating maximal symptoms) is 40.

3.3. Secondary Outcomes

The secondary outcomes include the following:

- The severity of bronchoconstriction (measured by maximum percent fall in FEV₁) during the aspirin-induced reaction at Visit 2, compared between patients on placebo vs ifetroban.
- Increase in urinary and nasal levels of cysLTs during aspirin-induced reaction at Visit 2 from Visit 2 pre-aspirin levels, compared between patients on placebo vs ifetroban, as a proof-of-mechanism that TP receptor signaling in AERD drives cysLT overproduction.
- Change in levels of other urinary and nasal eicosanoids, and levels of plasma/serum and nasal tryptase, both from Visit 1 to Visit 2 prior to aspirin administration and also from Visit 2 prior to aspirin administration to during aspirin-induced reactions at Visit 2, compared between patients on placebo vs ifetroban.
- Change in numbers/percentages of activated platelets and platelet-leukocyte aggregates in the peripheral blood between Visit 1 and Visit 2 baseline (pre-aspirin administration) and Visit 2 baseline and during the aspirin-induced reaction at Visit 2, compared between patients on placebo vs ifetroban.

- Change in baseline (pre-aspirin administration) FEV₁, Asthma Control Questionnaire (ACQ), and Sino-Nasal Outcome Test (SNOT-22) at Visit 2 from Visit 1, compared between patients on placebo vs ifetroban.
- Change in Visit 2 baseline (pre-aspirin administration) levels of exhaled nitric oxide (FeNO) from Visit 1, compared between patients on placebo vs ifetroban.
- For each secondary endpoint above, which compares the aspirin-induced changes during the aspirin-induced reaction at Visit 2 for patients on placebo vs ifetroban, we will also analyze these changes with provocative aspirin dose as a covariate. We will treat provocative aspirin dose as level variable: in log scale, if the aspirin doses are 40.5, 81, 162, and 325, we will code the dose variable as dose 1, 2, 3 and 4 assume each increase in dose is linear.

3.4. Exploratory Outcomes

The exploratory outcomes include the following:

- Plasma and nasal lavage levels of IL-33, and platelet products, as measured at baseline (pre-aspirin administration) and during aspirin-induced reactions at Visit 2, compared between patients on placebo vs ifetroban.
- Other inflammatory mediator levels in plasma, nasal lavage, and urine, as measured at baseline (pre-aspirin administration) and during aspirin-induced reactions at Visit 2, compared between patients on placebo vs ifetroban.
- Levels of surface expression of eicosanoid receptors by effector cells (eosinophils, basophils, and ILC2s) in the peripheral blood at baseline (pre-aspirin administration) and during the aspirin-induced reaction at Visit 2, compared between patients on placebo vs ifetroban.
- For each exploratory endpoint above, which compares the aspirin-induced changes during the aspirin-induced reaction at Visit 2 for patients on placebo vs ifetroban, we will also analyze these changes with provocative aspirin dose as a covariate. We will treat provocative aspirin dose as level variable: in log scale, if the aspirin doses are 40.5, 81, 162, and 325, we will code the dose variable as dose 1, 2, 3 and 4 assume each increase in dose is linear.

3.5. Stratification, Randomization, and Blinding/Masking

We will use block randomization in groups of four, ensuring that equal numbers of subjects are randomized to each group. For this two-arm balanced-design study, the randomization will consist of blocks of 4 patients randomly assigned (allocation ratio of 1:1) to ifetroban or placebo. Matching capsules of ifetroban and placebo will be supplied by Cumberland Pharmaceuticals and provided to the BWH Investigational Drugs Services pharmacy (IDS) for storage and distribution. The IDS will conduct the randomization and keep records to maintain study blinding.

3.5.1. Procedure for Unblinding/Unmasking

Unblinding must be approved by the study Medical Monitor unless an immediate life threatening condition has developed and the Medical Monitor is not accessible. In case of an emergency where a subject needs to be unblinded, the PI or physician co-investigators may contact IDS to unblind the subject. The IDS pharmacist is on call 24 hours a day. The PI will notify the protocol chair of the unblinding event on the next business day.

A full account of the event will be recorded, including the date and time of the unblinding, the reason for the decision to unblind, and the name of the individual who made the decision and the names of the Medical Monitor and others who were notified. The reasons for unblinding of a participant's treatment will be included in the final study report.

Unblinding of the entire study will require written approval from NIAID.

4. Selection of Participants and Clinical Sites/Laboratories

